**VIII. Statistical analysis**

**IX. Measures of quality control**

**X. Expected research results**

**XI. Potential risks, benefits or advantages of this study**

**XII. Data preservation and confidentiality**

**XIII. Measures to protect subjects and minimize risks**

## I. Background

Blue rubber bleb nevus syndrome (BRBNS) is a rare systemic syndrome featuring venous malformation and hemangiomas. Affected organs include skin and gastrointestinal tract. Patients manifest venous malformation (VM) at birth. Main histologic features of VM are dilated and distorted veins surrounded by sparse and irregular smooth muscle cells. The size and number of VM lesions in BRBNS increase gradually with age. Patients' skin develops 1-2cm of blue-violet, compressible, and hyperkeratotic VM lesions, mostly in palms and soles. Lesions cause local deformity, pain and intravascular coagulopathy. The latest manifests elevated D-dimers and may lead to disseminated intravascular coagulation (DIC). Risk of DIC is even higher under surgical treatment. Lesions of BRBNS can be found in the mucosa of the whole gastrointestinal tract. Small intestine is the most commonly affected organ. Lesions can cause gastrointestinal bleeding, intussusception, intestinal torsion and even intestinal necrosis. Due to long-term chronic gastrointestinal bleeding, many patients need to take life-long iron supplementary treatment and receive blood transfusions repeatedly. VM lesions of BRBNS can also affect organs in pelvic, abdominal and thoracic cavity. BRBNS is such a devastating disease, traditional drugs such as glucocorticoids, interferon- $\alpha$ , propranolol and intravenous iron are not effective. Besides surgical resection of affected tissue and repeated sclerotherapy, there is no validated targeted drug treatment.

Sporadic BRBNS cases have been reported. There are also a few familial cases consistent with autosomal dominant inheritance pattern. Soblet et al show that BRBNS is caused by somatic mutation of TEK gene, which encodes a receptor of angiogenin, endothelial tyrosine kinase receptor TIE2. Multifocal VM lesions of BRBNS patients are caused by double (*cis*) mutations, i.e., two somatic mutations on the same allele of the gene. Germline mutations of TEK gene can cause venous malformation, cutaneous and mucosal (VMCM), a rare autosomal dominant hereditary disease. Several repetitive mutation sites of TEK gene have been observed in sporadic BRBNS patients. These mutations result in ligand-independent activation of TIE2 and PI3K/AKT signaling pathways, which in turn promote cell survival, migration, invasion and colonization.

In addition to multifocal VM lesions, Soblet et al. also found that about 20% of unifocal VM patients carry PIK3CA gene (encoding Class I p110 $\alpha$  catalytic subunit of PI3K) mutation, which also activates the PI3K/AKT signaling pathway. Clinically, venous malformation diseases caused by TIE2 and PIK3CA somatic mutations are almost indistinguishable, suggesting that the PI3K/AKT signaling pathway plays a key role in BRBNS.

An important protein kinase mTOR (mammalian target of rapamycin) downstream of the PI3K/AKT pathway can serve as a potential therapeutic target for the venous malformation syndromes mentioned above. Experiments on mice have shown that mTOR inhibitor rapamycin can control the progression of VM lesions. It can also relieve VM lesions caused by PIK3CA and TEK mutations in humans. There are a few cases reported using rapamycin (sirolimus) as treatment, and achieving satisfactory effects without significant adverse events. Large-scale prospective studies are needed to demonstrate the efficacy of rapamycin for BRBNS.

## II. Objective

1. To evaluate the safety of sirolimus in treatment of blue rubber blisters syndrome (BRBNS), hereditary cutaneous and mucosal venous malformation (VMCM), and sporadic multiple VM.
2. To evaluate the efficacy of sirolimus in treatment of blue rubber blisters syndrome (BRBNS), hereditary cutaneous and mucosal venous malformation (VMCM), and sporadic multiple VM.

### **III. Research Design**

1. This study is a prospective, nonrandomized, open-label, single-arm clinical trial. The sirolimus capsule (Rapamycin, Yixinke®), 0.5 mg/grain\*20/box, is produced by North China Pharmaceutical Co., Ltd.
2. All patients who meet inclusion criteria and sign informed consents receive sirolimus treatment for at least 6 months. Patients are followed up in a regular schedule.
3. No less than 20 patients should be enrolled.

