### **B. Evaluation during sirolimus treatment**

Adverse reactions are evaluated weekly during the first month of drug treatment. The efficacy and safety are then evaluated at the 3rd and 6th months, and the content of the examination is the same as the pre-trial evaluation.

- 1) Efficacy assessment:
  - a. Clinical symptom assessment (including VAS pain score, gastrointestinal bleeding, quality of life (Qol) evaluation, frequency of blood transfusion treatment and other related symptoms);
  - b. Changes in hemoglobin;
  - c. Coagulation I+D-dimer examination;
  - d. Nutritional status (including albumin, etc.);
  - e. Ultrasound, MRI examination of the lesion, abdominal and pelvic cavity contrast-enhanced CT + small intestine reconstruction CT examination, digestive system endoscopy to measure the size, quantity and total load of VM lesions;
- 2) Safety assessment: Safety parameters (such as asking adverse events, measuring laboratory values, vital signs, gastrointestinal bleeding, etc.) will be closely monitored on a regular basis throughout the study.
- 3) Treatment compliance: In order to monitor compliance, subjects are required to complete an electronic diary during the entire study period. Dates of drug intake will be tracked by this diary. At every visit, the investigator and the subject will review the electronic diary data together.

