### **C. Evaluation after treatment**

Evaluation of curative effects and safety is conducted at the end of the drug therapy, six and twelve months after the treatment. Its content is the same as pre-trial evaluation.

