#### **D. Evaluation of the relationship between adverse reactions and experimental drug**

According to the 5-level judgment system, the relationships can be divided into 5 types: definitely related, very likely related, may be related, may be irrelevant, and definitely irrelevant. The first three are counted as adverse reactions, in which case the incidence of adverse reactions and adverse events should be reported.

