### **A. Methods of statistical analysis**

The categorical variables will be described by frequency distribution (number of cases and percentage). Continuous variables will be described with mean, median, minimum, maximum, first and third quartile. The confidence interval of all parameters is set to be 95%. All analyses will be conducted with SPSS.

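### Adverse-event incidence would pool unequal treatment durations, because treatment has a 6-month minimum, no maximum and no defined risk window

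*Combined protocol and SAP*

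**What the plan says.** **Duration.** Section III (Research Design) says that patients "receive sirolimus treatment for at least 6 months". It sets a floor and no ceiling. The adult regimen in V.C ends with a second 3-month period and a reassessment, and does not say what follows. Exposure can also be shorter than 6 months: the exit criteria (IV.C) and V.C allow withdrawal for allergy, patient request, compliance, safety, surgery or intolerance.

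**Safety result.** The section of VII on relationship to the drug says "the incidence of adverse reactions and adverse events should be reported". VIII.B item 3 confines the analysis to side effects and events while the patient is on medication. VIII.A gives one summary for data of this type: "The categorical variables will be described by frequency distribution (number of cases and percentage". No person-time rate, time-to-event method or fixed risk window appears.

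**Visits.** VI.B says "The efficacy and safety are then evaluated at the 3rd and 6th months", after weekly adverse-reaction checks in the first month. VI.C adds: "Evaluation of curative effects and safety is conducted at the end of the drug therapy, six and twelve months after the treatment". VIII.B item 2 names no efficacy time point.

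**Exposure data.** Under VI.B item 3, patients keep an electronic diary: "Dates of drug intake will be tracked by this diary".

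**The concern.** A percentage of patients with an event can be interpreted only if the period at risk is known. Under this plan that period is each patient's own time on drug, which may be a few weeks, 6 months or much longer. Two trials of the same drug with the same toxicity could then report different incidences only because one kept patients on treatment longer.

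There is no control arm with similar exposure to offset this, so the percentage has to stand alone. Safety is Objective 1. The planned 95% confidence interval does not help, because it describes sampling error and not the undefined window.

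A narrower version affects efficacy. The evaluation at the end of treatment, and those 6 and 12 months after it, fall at different times since first dose in different patients, and the plan does not say which reading is the main one.

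**Working it through.** The documents give no event rate, distribution of durations or derived sample size, so there is no figure of theirs to reproduce. The check is whether the stated summary depends on treatment length, and by how much under stated assumptions.

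**Inputs**
- From the documents: minimum duration 6 months, no maximum (III); summary by count and percentage (VIII.A); at least 20 patients (III).
- Assumed: a constant first-event rate h of 2%, 3% or 5% per patient-month; durations of 6, 12 or 18 months; half the patients in each duration group.

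**Step 1. Risk by duration.** Risk(t) = 1 − exp(−h·t). At h = 0.03:
- 6 months: 1 − exp(−0.18) = 16.5%
- 12 months: 1 − exp(−0.36) = 30.2%
- 18 months: 1 − exp(−0.54) = 41.7%

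**Step 2. Pooled percentage.**
- Half 6, half 12 months: (16.5 + 30.2)/2 = 23.4% from unrounded values, 1.4 times the 6-month risk.
- Half 6, half 18 months: (16.5 + 41.7)/2 = 29.1%, 1.8 times the 6-month risk.

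| Assumed rate per month | Risk at 6 months | Half 6, half 12 | Half 6, half 18 |
|---|---|---|---|
| 2% | 11.3% | 16.3% | 20.8% |
| 3% | 16.5% | 23.4% | 29.1% |
| 5% | 25.9% | 35.5% | 42.6% |

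**Step 3. When the effect is small, or reversed (h = 0.03).**
- If only 10% of patients continue to 18 months and the rest stop at 6: 0.9 × 16.5 + 0.1 × 41.7 = 19.0%.
- If no first events occur after month 6, the pooled figure stays at 16.5% whatever the later duration.
- Early exit works the other way. If a quarter leave at month 3 for unrelated reasons, the 3-month risk is 1 − exp(−0.09) = 8.6%, and the pooled figure is 0.25 × 8.6 + 0.75 × 16.5 = 14.5%.

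**Step 4. Person-time rate.** Expected time at risk per patient is Risk(t)/h. For half 6 and half 18 months it is (0.165/0.03 + 0.417/0.03)/2 = 9.7 months, and 0.291/9.7 = 0.030 per month. For half 6 and half 12 it is 7.8 months, and 0.234/7.8 = 0.030. Under a constant rate, this measure does not move with the mix of durations.

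**Step 5. Against sampling error.** With 4 events in 20 patients (20%), the exact 95% interval is 5.7% to 43.7%. Shifts of the size in Step 2 lie within the noise of a trial this small. They are still systematic, and the interval does not reflect them.

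**The case against.** The best defence is that the trial is small and descriptive, and that its written schedule points to month 6. The adult dosing steps, the drug-level tests and the scheduled on-treatment visits all end there. If treatment mostly ends there too, the problem nearly disappears. VIII.B item 3 does supply an on-treatment window, though one that varies by patient. That the result will be a simple proportion is inferred from VII and VIII.A read together; no denominator is stated. The illustrative figures rest wholly on an assumed constant rate, assumed durations and an equal split. All of this stands, and it limits the size of the point. It does not give the percentage a defined time window.

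Three stronger readings are tempting, and the documents do not support them.

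- **That patients who respond stay on drug longer.** Nothing ties treatment length to response. V.C ties only the adult dose to improvement at month 3, and the written reasons for early exit do not include non-response. The safety point needs only unequal duration.
- **That late events are captured less completely.** Scheduled on-treatment visits do stop at month 6 until treatment ends. But VI.B item 2 promises regular safety monitoring throughout the study, VI.C adds later safety evaluations, and VII requires events to be followed until resolved. Poorer late capture is a possibility, not a consequence of the plan.
- **That efficacy as a whole mixes unequal exposure.** The full examination set is repeated at months 3 and 6, so every patient still on study has readings at common times. Nothing says that the end-of-treatment reading is the main one or will be pooled with others.

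**Conclusion.** The point holds for safety. Followed as written, the plan would give adverse-event percentages over patient-specific exposure with no defined time window. For efficacy there is only a secondary gap: common-time readings exist, but none is named as the main one.

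The size cannot be determined from the documents. At an assumed constant 3% per month, a 6-month risk of 16.5% would be reported as about 23% or 29% under the two half-and-half mixes. Front-loaded toxicity would make the shift smaller, and it would nearly vanish if most patients stop at month 6. This is a worthwhile improvement at almost no cost, not a flaw that undermines the trial.

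**What to change.** **VIII.B item 3 (main change).** Report adverse events and adverse reactions in two ways:

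- (a) From first dose to month 6, in all treated patients. State how exits before month 6 are handled, for example by a Kaplan-Meier estimate, or by a cumulative-incidence estimate with exit as a competing event.
- (b) As a rate per patient-month on drug over all exposure, using the diary intake dates. Split it into before and after month 6, because a single overall rate is interpretable only if the rate is roughly constant.

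Tabulate treatment duration and dose alongside.

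**VIII.B item 2 (secondary change).** Name the existing month-6 visit as the common efficacy time point. Show results at the end of drug therapy separately, with treatment duration. Month 6 equalises time since first dose but not dose, since the adult dose may change after month 3; the dose table covers this.

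**Cost.** Wording in the analysis section and one extra table. The diary already records exposure dates and the month-6 visit is already scheduled. No new visit, data item or treatment rule is needed.

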### **IV. Selection of subjects**

#### **A. Inclusion criteria**

- (1) Patients diagnosed with BRBNS, VMCM, sporadic multiple VM, or large single VM;
- (2) Age and gender are not limited;
- (3) Physical status ECOG 0~3;
- (4) Organ function is good, biochemical examination meets the following conditions:
  - a) AST  $\leq 2.5 \times$  upper limit of normal value (ULN),
  - b) ALT  $\leq 2.5 \times$  upper limit of normal value (ULN),
  - c) serum total bilirubin  $\leq 1.5 \times$  upper limit of normal value (ULN),
  - d) creatinine  $\leq 1.5 \times$  upper limit of normal (ULN);
- (5) Patients volunteer to participate in the trial. Participant or his/her legal guardian signs the informed consent form.

#### **B. Exclusion criteria**

- (1) Patients need emergency surgery due to intestinal obstruction, intussusception, or gastrointestinal bleeding;
- (2) History of surgery within 1 month;
- (3) Allergic to rapamycin;
- (4) Any disease or condition that may affect the study implementation or result interpretation, including:
  - a) known hemoglobinopathy
  - b) concomitant gastrointestinal infections
  - c) severe heart, liver, kidney and other serious concomitant diseases that may endanger lives
- (5) Pregnant or lactating women;
- (6) Alcohol or drugs (eg, laxatives) abusers;
- (7) Participate in another clinical trial that may affect his or her study within one month;
- (8) The investigator believes to be not suitable for other reasons.

### **C. Exit criteria**

- (1) An allergic reaction occurs.
- (2) The patient requests withdrawal: at his or her own discretion or at the request of his or her legal representative. Subjects may refuse to participate in further studies at any time without providing reasons. Subjects will not be affected because of such decision.
- (3) Subjects are required to withdraw from the study in certain special circumstances (eg, there is significant issues of compliance, safety, or surgery for venous malformations)
- (4) Other situations in which the study must be terminated. For example, the investigators believe that continuing the study may be harmful to the health of subjects.

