### **D. Rejection criteria**

- (1) Patients who violate the requirements of the test protocol
- (2) Patients with poor-recording, incomplete, or inaccurate data

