### **B. Contents of statistical analysis**

- 1) General data analysis: Demographic variables and baseline characteristics will be summarized comprehensively by mean of descriptive statistics and/or appropriate frequency tables.
- 2) Evaluation of efficacy: According to follow-up and reexamination results, the patients' quality of life, size and volume of the lesions, tumor load control and improvement of symptoms will be analyzed.
- 3) Analysis of adverse events: Side effects and adverse events during medication will be assessed.
- 4) Evaluation of the relationship between adverse events and the tested drug

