## **XI. Potential risks, benefits or advantages of this study**

As a drug that has been on the market for years, it is applied to this study beyond its indication. It is recommended by doctors considering that its benefits outweigh its risks and the subjects have no better choice. For subjects, it may relieve their symptoms and improve quality of life, and complications associated with surgery and damage to intestinal function can be avoided. The testing drug is free during the study and subjects should bear the risks of treatment.

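### Patients who have surgery for venous malformations on sirolimus must withdraw and can drop out of the efficacy summary, because the plan has no rule for scoring the operation or for setting aside values measured after it

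*Combined protocol and SAP*

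**What the plan says.** All references are to the combined protocol and SAP.

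- **Design (Section III).** "This study is a prospective, nonrandomized, open-label, single-arm clinical trial". On size: "No less than 20 patients should be enrolled".
- **Exit (IV.C, item 3).** Withdrawal is required in special circumstances, of which the examples are that "there is significant issues of compliance, safety, or surgery for venous malformations". The operation is thus grouped with compliance and safety problems.
- **Rejection (IV.D, item 2).** One ground is "Patients with poor-recording, incomplete, or inaccurate data". No exception is made for data that are incomplete because the patient exited.
- **Efficacy assessments (VI.B).** Efficacy is evaluated at months 3 and 6. The symptom items are "Clinical symptom assessment (including VAS pain score, gastrointestinal bleeding, quality of life (Qol) evaluation, frequency of blood transfusion treatment and other related symptoms". The others are hemoglobin, coagulation with D-dimer, nutritional status, and lesion size, number and load from imaging and endoscopy. An operation is not an item.
- **After treatment (VI.C).** "Evaluation of curative effects and safety is conducted at the end of the drug therapy", and again six and twelve months later. Whether this covers patients who exited is not stated.
- **Efficacy analysis (VIII.B, item 2).** Besides quality of life, "size and volume of the lesions, tumor load control and improvement of symptoms will be analyzed". Section VIII defines no analysis set, no responder, and no rule for missing data or for surgery during treatment.
- **Potential benefit (XI).** Among the possible gains for subjects, the plan says that "complications associated with surgery and damage to intestinal function can be avoided".

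**The concern.** Section I names resection as one of the existing options for this disease, and Section XI hopes that sirolimus will spare patients the harm of surgery. A patient who needs an operation for venous malformations while taking the drug is therefore likely, though not certain, to be one in whom it did not work well enough. The plan already treats the need for one other intervention, transfusion, as an efficacy item, but not the need for surgery.

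The exit and rejection rules, taken together, allow that patient to leave the efficacy result without being scored. If the patient is instead imaged after the operation, resection itself lowers lesion size, number and load, and nothing in the plan flags those values. In an uncontrolled, open-label trial no comparison group suffers the same loss, so any distortion passes straight into the reported response. A choice made after the data are seen would also be open to selective handling.

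**Working it through.** **Step 1. What happens to an operated patient under the text as it stands.**

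| Time of operation | Month-3 value | Month-6 value | Rule for scoring |
|---|---|---|---|
| Before month 3 | None before surgery is guaranteed | None after exit, unless still examined | None |
| Between months 3 and 6 | Yes, before surgery | None after exit, unless still examined | None |

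In both rows the record is incomplete at month 6, so IV.D(2) can be applied. If the end-of-therapy evaluation in VI.C is carried out after the operation, the lesion measurements are post-resection. No row leads to a score of not improved.

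**Step 2. Inputs for an illustration.** From the plan: N = 20 (the minimum in Section III) and 95% confidence intervals (VIII.A). Assumed, because the plan gives neither a response rate nor a surgery rate: x patients improve without surgery, and k of the others have surgery by month 6 and have not improved.

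The three handlings are:
- dropped: x/(20 − k)
- scored improved after resection: (x + k)/20
- counted as not improved: x/20

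**Step 3. Main case, x = 10 and k = 2, exact (Clopper-Pearson) intervals.**
- Dropped: 10/18 = 55.6% (30.8 to 78.5)
- Scored improved: 12/20 = 60.0% (36.1 to 80.9)
- Not improved: 10/20 = 50.0% (27.2 to 72.8)

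The excess over the third handling is 5.6 points if dropped and 10.0 points if scored improved.

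**Step 4. Range over the assumptions.**

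| k | x = 10: dropped | x = 10: scored improved | x = 14: dropped | x = 14: scored improved |
|---|---|---|---|---|
| 1 | 52.6% | 55.0% | 73.7% | 75.0% |
| 2 | 55.6% | 60.0% | 77.8% | 80.0% |
| 3 | 58.8% | 65.0% | 82.4% | 85.0% |
| 4 | 62.5% | 70.0% | 87.5% | 90.0% |
| 5 | 66.7% | 75.0% | 93.3% | 95.0% |

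Counted as not improved, the result stays at 50.0% (x = 10) or 70.0% (x = 14) throughout.

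**Step 5. Direction if the operation follows a response.** Suppose instead that 12 patients improve and 2 of them then have an elective operation. The correct figure is 12/20 = 60.0%, and dropping the two gives 10/18 = 55.6%. The error now runs against sirolimus, so its direction depends on why the patient was operated on.

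**Step 6. Mean change in load (all percentages assumed).** Let 18 patients average −15%, and let the 2 operated patients be at +20% before and −60% after the operation.
- Dropped: −15.0%
- Post-operative values: (18 × (−15) + 2 × (−60))/20 = −19.5%
- Pre-operative values: (18 × (−15) + 2 × 20)/20 = −11.5%

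The last line needs a pre-operative measurement on treatment, which the schedule does not guarantee before month 3.

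**Step 7. Is the rule likely to be needed?** The chance of at least one operation among 20 patients is 1 − (1 − r)^20. For assumed per-patient rates r of 5%, 10% and 20% this is 64%, 88% and 99%.

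**The case against.** Several points on the other side have force.

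- **The plan nowhere says that exited patients are excluded.** True. Exclusion follows from required withdrawal, the rejection of incomplete data and the lack of an analysis set. A patient operated on after month 3 still has a month-3 value. The loss is thus possible under the text, not certain, and need not affect both time points.
- **Post-operative scoring is conditional.** VI.C does not say that withdrawn patients are examined, and VIII.B has no responder definition by which they would count as improved. This stands. The point is only that nothing prevents it.
- **Not every operation is a drug failure.** A reader might infer that any handling other than failure must favour sirolimus. The documents do not support that: IV.C does not separate planned, elective or response-enabled surgery, and early post-operative pain, hemoglobin or quality of life could be worse, not better. Step 5 shows the opposite direction.
- **Surgery avoidance is not an objective.** A reader might infer that the trial fails to test a promised benefit. Section XI offers it only as a potential benefit, Section II does not list it, and a single arm with no planned comparison rate could not show it even if operations were counted.
- **The shift is small beside the uncertainty.** In the main case it lies inside the interval of 27.2% to 72.8%, and the plan has no success threshold to cross. Exclusion at entry of patients needing emergency surgery (IV.B) may also keep operations few. Both are fair, but bias and imprecision are separate problems, and this bias can be removed cheaply.
- **Operations need not go unseen.** Hospitalization makes an event serious under Section VII, and bleeding and transfusion are efficacy items. That puts the operation on record as safety or symptom data but does not say how the patient counts for efficacy.

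**Conclusion.** The concern holds in a limited form. The exit and rejection rules, with no scoring rule for surgery, allow operated patients to fall out of the month-3 or month-6 efficacy summary, and nothing bars post-resection measurements from being read as a drug effect. Where the operation reflects lack of response, the result is too favourable, with no control arm to offset it.

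On 20 patients with 10 improved and 2 operated on without improving, the overstatement is 5.6 to 10.0 percentage points. Only the 20 comes from the plan. The other counts are assumptions, and with no operations the effect is nil.

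The documents do not show that operated patients will be excluded, that they will be scored as improved, or that every operation is a failure. The gap should be closed before efficacy data are examined.

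**What to change.** Add the following to VIII.B(2).

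1. **Proportions.** Keep all treated patients in the denominator. Do not apply IV.D(2) to patients whose data are incomplete because of surgery for venous malformations. By default, count a patient who has such surgery by the time point analysed as not improved in every improvement and load-control proportion. Record the date and reason for surgery on the case report form, since no section now requires the reason for exit to be recorded. Add a sensitivity analysis for operations that were planned or made possible by response.
2. **Continuous measures.** Do not use post-operative lesion, pain or quality-of-life values as sirolimus effects. Use pre-operative on-treatment values where they exist, and state how many operated patients have none.
3. **Operations.** Report the number and percentage of treated patients having surgery for venous malformations by month 6, with an exact 95% interval. For example, 2/20 would be 10% (1.2 to 31.7). Label this as descriptive, because a single arm cannot show that surgery was avoided.

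The cost is one or two case-report fields, some analysis wording and a slightly less favourable reported response. The default in item 1 misclassifies any patient operated on after a response, which is what the sensitivity analysis is for. No extra visit is needed and no change to the clinical exit rule is proposed.
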